4.3 **Criteria for considering participants “enrolled.”** Individuals will be considered enrolled in the study at the point of randomization to a study arm in the CET. Randomization will occur after oral consent to participate and completion of baseline assessments. People who do not complete oral consent and randomization will not be considered fully enrolled and will be replaced until 50 people are randomized in the CET (25 in each arm).

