PROTOCOL TITLE: Comparative Effectiveness Trial of Tobacco Cessation Treatments among Cancer Patients who Smoke

the application). The interview will address the participants' cancer experiences, tobacco use history, smoking and supportive care outreach, and smoking treatment. The interview outline is uploaded with the application. These interviews will be recorded and transcribed without participant identifying information.

Oral consent. In the oral consent process, UW-CTRI study coordinators will read the oral informed consent script to participants and will then ask if they have any questions. The study coordinator will answer questions during the call, or will schedule a follow-up call if the patient needs more time to make a decision about the study or if the study coordinator needs to consult with the PI or other team member to address the patient's concerns or questions. Once the patient's questions have been fully addressed, the patient will be asked questions to assess their comprehension of key CET study features. People who are unable to answer these questions correctly, even after review of key points by the study coordinator, will be considered unable to consent and will be referred to their care team and given information about WTQL services. Those who pass the comprehension screening will be asked if they consent to participate in the CET study.

Baseline assessment. Next, participants will complete a baseline assessment (see uploaded survey) of their tobacco use history, nicotine dependence, quitting motivation, quitting confidence, stress, mood, wellbeing, quality of life, support system, symptom burden, and demographics. Participants will also select a target date to quit smoking within the next 60 days at this call. These activities will occur during the enrollment phone call if participants are willing and able to stay on the call. If they are not, the UW-CTRI study coordinator will schedule this assessment call within the following 1-2 weeks.

Randomization. Participants will next be randomized to treatment. Participants will be considered fully enrolled once consented, baseline assessment is complete, and randomized. Study coordinators and participants will be informed of the randomly assigned condition after the baseline assessment is completed.

Treatment procedures. These are described in section 13.1 above.

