Follow-up assessments. UW-CTRI follow-up assessors will call CET participants 12 and 26 weeks after their target quit dates to collect outcome data (see uploaded follow-up surveys) including: tobacco use; quitting motivation and confidence; stress, mood, wellbeing, quality of life, support, and symptom burden; and treatment utilization, satisfaction, and adverse events. In addition to these self-report measures, counseling utilization and medication refill data will be used to track smoking treatment adherence; EHR data on healthcare utilization and diagnoses will be extracted (with patient consent provided at enrollment); and biochemical verification of abstinence claims at the 6-months post-quit follow-up

PROTOCOL TITLE: Comparative Effectiveness Trial of Tobacco Cessation Treatments among Cancer Patients who Smoke

will be obtained via carbon monoxide breath samples and urinary cotinine samples, or mailed saliva samples (as participants are able to provide them).

13.2 CET procedure schedule.

Study Phase	Enroll- ment	Treatment/Intervention Calls								Follow Up Calls	FU Visit
Study Contact	1	2	3	4	5	6	7	8	9	10	11
Week relative to target quit day (tqd, day 0)	-8 to -3	-1	0 tqd	1	2	4	8	12	12	26	26-29
Eligibility screening	✓										
Oral informed consent & HIPAA Authorization	✓										
Clinician(s) given 5 business days to disapprove study medication; medications dispensed if not disapproved	✓										
Tobacco, alcohol, and cannabis history	✓										
Nicotine dependence	✓										
Motivation to quit	✓	✓	✓	✓					✓	✓	
Quitting confidence	✓	✓	✓	✓					✓	✓	
Stress, mood, and withdrawal		✓	✓	✓					✓	✓	
Wellbeing and quality of life	✓								✓	✓	
Social support	✓								✓	✓	
Demographics	✓										
Randomization	✓										
Welcome mailing packet with study information sheet sent	✓										
Standard care (SC) counseling (10-15 minutes)		SC	SC	SC							
Standard care nicotine patch treatment (2 weeks)			SC	SC							
Enhanced care (EC), cancer-specific counseling		EC	EC	EC	EC	EC	EC	EC			
Enhanced care varenicline treatment (12 weeks)		EC	EC	EC	EC	EC	EC	EC			

PROTOCOL TITLE: Comparative Effectiveness Trial of Tobacco Cessation Treatments among Cancer Patients who Smoke

beginning with run-in period 1 week pre-quit followed by 11 weeks at full dose post-quit, as per package insert)										
Recent tobacco, alcohol, and cannabis use								✓	✓	✓
Treatment use								✓	✓	✓
Treatment satisfaction								✓	✓	

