In this pilot study, we seek to demonstrate the feasibility and acceptability of the proactive outreach model as a way to enhance the reach of smoking treatment, and as a feasible way to recruit participants for a CET of enhanced vs. standard smoking cessation treatment. We also hope to generate estimates of enhanced vs. standard treatment effects on biochemically verified 7-day point-prevalence abstinence rates 6 months after a target quit date (primary outcome) and other abstinence measures (e.g., self-reported prolonged and point-prevalence abstinence 3 and 6 months post-quit). As such, we selected a sample size of 50 to generate stable estimates of the size of treatment effects on these outcomes and costs,

PROTOCOL TITLE: Comparative Effectiveness Trial of Tobacco Cessation Treatments among Cancer Patients who Smoke

and to permit exploration of differences in treatment effects by sex, race, ethnicity, and disadvantage. A sample of 50, while too small to sensitively test for moderate treatment benefits, is sufficient to pilot test all study and treatment procedures and to yield informative effect estimates that will guide a future, full-scale CET of standard and enhanced care.

The primary outcome will be analyzed in an intent-to-treat analysis in which all randomized participants are included, and missing cases are assumed to be non-abstinent. This will be supplemented by sensitivity analyses that again use the full sample of randomized participants to examine robustness of results across different assumptions regarding missingness. Multiple imputation will not be used in this pilot project.

For the qualitative study, we will recruit as many participants as we can until we reach thematic saturation in qualitative data coding. We anticipate that this will occur with fewer than 32 participants.

20.3 Participant Population(s) for Analysis.

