We will examine reach of the treatment by computing the proportion of all participants meeting inclusion criteria for proactive tobacco outreach who were referred to WTQL, referred to their PCP, and the proportion who were screened for, eligible for, and enrolled/randomized in the CET. As such, the pool of participants for Aim 1 includes everyone eligible for inclusion on at least 1 CRDS report that guides proactive tobacco treatment outreach. The pool of participants included in Aims 2, 3 and 5 will comprise all participants who were randomized to treatment in the CET. The pool for Aim 4 will include all participants who participated in a qualitative interview.

20.4 Statistical Methods.

Descriptive statistics will be used to characterize smoking treatment reach (the proportion of eligible patients who initiate any smoking cessation treatment, and the proportion who enroll in the CET. These rates will be computed overall, and by patient subpopulation.

Logistic regression will be used to estimate the effects of treatment condition on binary outcome data (e.g., abstinence, side effects), overall and by patient subgroups (i.e., moderation effects). Odds ratios and numbers needed to treat will be computed to estimate treatment effect sizes.

Analyses of variance will be used to examine condition effects on continuous variables such as ratings of treatment satisfaction, burden, and treatment effects on ratings of patient experiences and candidate treatment mediators (e.g., withdrawal). Treatment effect sizes will be computed. Cost-effectiveness will be calculated based on the incremental cost-effectiveness

PROTOCOL TITLE: Comparative Effectiveness Trial of Tobacco Cessation Treatments among Cancer Patients who Smoke

ratio of enhanced treatment versus standard treatment per each additional case of abstinence.

Thematic analysis of qualitative interview will identify themes that emerge in patient interviews in the following areas: cancer experiences, supportive care outreach, tobacco history, and tobacco treatment.

20.5 Planned Interim Analysis.

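### Section 20.4 names no baseline covariate for continuous outcomes, although several repeated scales have a pre-randomisation value that would tighten exploratory estimates at no cost

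*Combined protocol and SAP*

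**What the plan says.** **Method.** Section 20.4 states: "Analyses of variance will be used to examine condition effects on continuous variables". Its examples are satisfaction with treatment, burden, what patients report experiencing, and possible mediators, with withdrawal as the example. The list is illustrative. Neither 20.4 nor any other section mentions a baseline covariate, ANCOVA or change from baseline.

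**What is measured before randomisation.** Section 13.1 (Baseline assessment) lists "nicotine dependence, quitting motivation, quitting confidence, stress, mood, wellbeing, quality of life, support system, symptom burden, and demographics", along with tobacco use history. Sections 4.3 and 13.1 place randomisation after the baseline assessment is complete.

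**What is measured again.** The follow-up text in 13.1 repeats motivation, confidence, stress, mood, wellbeing, quality of life, support and symptom burden at 12 and 26 weeks. The schedule in 13.2 ticks motivation, confidence, wellbeing/quality of life and social support at enrolment and at both follow-up calls.

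**Where the two differ.** The schedule row "Stress, mood, and withdrawal" has no tick at enrolment. Its first tick is contact 2, one week before the target quit date. The baseline text does list stress and mood, but not withdrawal. Symptom burden appears in the text of 13.1 and has no schedule row.

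**Purpose of the sample.** Section 20.2: "we selected a sample size of 50 to generate stable estimates of the size of treatment effects on these outcomes and costs". It also concedes: "A sample of 50, while too small to sensitively test for moderate treatment benefits".

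**The concern.** In a randomised comparison of a scale measured before and after treatment, the pre-randomisation score is usually the best single predictor of the follow-up score. Regressing follow-up on arm plus that score removes the variation it explains and corrects the estimate for whatever imbalance chance produced at enrolment. A comparison of follow-up means alone does neither.

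This matters more than usual here, because the trial is small and exists to supply estimates for planning a larger one. Intervals on the repeated scales will be wide in any case, and the data that would narrow them are already being collected. Leaving the model open also permits a later choice among raw, change-score and adjusted results once the data have been seen.

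A related trap is the week -1 reading of stress, mood and withdrawal. An analyst looking for a baseline might take it, but it falls after randomisation, after participants have been told their arm (13.1), and at the point where varenicline starts in the enhanced arm (11.1).

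**Working it through.** **1. Inputs from the documents.** 50 randomised, 25 per arm (4.3); analysis of variance with no covariate named (20.4); baseline completed before randomisation (4.3, 13.1). Section 20.2 gives no alpha, power, effect size or SD, so the figure of 50 cannot be re-derived beyond 25 + 25.

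**2. Assumptions not in the documents.** Results are in SD units (SD = 1), with 95% intervals. The enrolment-to-follow-up correlation ρ is 0.3 to 0.7. A scenario of 20 per arm allows for loss to follow-up.

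**3. Unadjusted comparison, 25 per arm.**
SE = √(2/25) = 0.283. With t = 2.011 on 48 df, half-width = 0.569.

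**4. ANCOVA, 25 per arm.**
SE = √[(2/25) × (1 − ρ²) × (1 + 1/46)], with t = 2.012 on 47 df. The term 1/46 is the expected cost of estimating the slope when the arms differ by chance at baseline.

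| ρ | 1 − ρ² | SE | 95% half-width | Change from 0.569 |
|---|---|---|---|---|
| 0 | 1.00 | 0.286 | 0.575 | 1% wider |
| 0.1 | 0.99 | 0.284 | 0.572 | under 1% wider |
| 0.3 | 0.91 | 0.273 | 0.549 | about 4% narrower |
| 0.5 | 0.75 | 0.248 | 0.498 | about 12% narrower |
| 0.7 | 0.51 | 0.204 | 0.411 | about 28% narrower |

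A simulation of 20,000 trials at each of ρ = 0.3, 0.5 and 0.7 gave ANCOVA standard errors of 0.273, 0.247 and 0.204, in agreement with the formula.

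**5. Sample-size equivalent.** Ignoring the small-sample term, 50/(1 − ρ²) gives about 55, 67 and 98 at ρ = 0.3, 0.5 and 0.7. These are large-sample figures and flatter the gain slightly; the half-widths above are the better guide.

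**6. With 20 per arm.** The half-width is 0.640 unadjusted, and 0.620, 0.563 and 0.464 with ANCOVA at the same three correlations. The relative gain is about the same.

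**7. Change scores are not a substitute.** In the same simulation the change-score SE was 0.334 at ρ = 0.3 (worse than unadjusted), 0.282 at 0.5 (equal to it) and 0.219 at 0.7 (worse than ANCOVA).

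**8. Which outcomes can gain.**
- Text and schedule both show an enrolment value: motivation, confidence, wellbeing/quality of life, social support.
- Text shows one but the schedule does not: stress and mood (no enrolment tick), symptom burden (no row).
- No enrolment value: treatment satisfaction (follow-up only), patient ratings of burden (a treatment acceptability measure in 3.4), and withdrawal (first reading at contact 2). The gain from own-baseline adjustment is zero for these.

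**The case against.** The best case against the point has four parts.

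*The outcomes named in 20.4 mostly have no baseline.* This stands for satisfaction, treatment burden and withdrawal. It does not dispose of the point, because the list is illustrative, patient experiences are among its examples, and no other method is given for the repeated continuous scales.

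*The scales that gain are not endpoints.* This also stands. Motivation, confidence, wellbeing, quality of life and social support do not appear in 3.4, even as exploratory endpoints. The sample-size rationale in 20.2 centres on abstinence and costs. This limits the importance of the point without removing it.

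*Silence is not exclusion.* Section 20.4 names a family of methods and does not describe the model, so a covariate is not ruled out. A reader might infer that the sponsor has decided against adjustment; the text does not show that. Still, an analyst following it literally would use no covariate.

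*The correlation is unknown and may be low.* By the schedule, enrolment is 3 to 8 weeks before the quit date and follow-up 12 or 26 weeks after it. The readings are therefore 15 (12 + 3) to 34 (26 + 8) weeks apart, across a quit attempt in patients with cancer. The lower end of the range may be the realistic one for some scales. If so, the gain is small, but at zero correlation the cost of adjusting is only 0.569 to 0.575.

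Three stronger readings are tempting and are not supported. The first is that every continuous comparison loses precision: those without an enrolment value do not. The second is that the unadjusted estimates are biased by chance imbalance: under randomisation they are unbiased, and their intervals already reflect that variation. The third is that the plan treats the week -1 reading as a baseline: no section says so.

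**Conclusion.** The point holds in a limited form. For the four measures with an enrolment value in both text and schedule, the stated analysis leaves available precision unused. With 25 per arm, the standardised 95% half-width would fall from 0.57 to about 0.55, 0.50 or 0.41 at correlations of 0.3, 0.5 or 0.7, with no gain at about 0.1 or below. The same would apply to stress, mood and symptom burden if they are in fact collected at enrolment.

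The size rests on a correlation the documents do not supply and, for the main figures, on complete follow-up. It bears on exploratory measures only. The primary and secondary abstinence endpoints are binary, are analysed by logistic regression, and are untouched. The amendment is worthwhile because it is nearly free; the trial's main conclusions do not depend on it.

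**What to change.** 1. Add one sentence to 20.4: each continuous follow-up outcome with a pre-randomisation enrolment value is analysed, at each follow-up time, by linear regression on arm plus that value, reporting the adjusted difference and its 95% interval.
2. State that treatment satisfaction, treatment burden and withdrawal are compared without baseline adjustment. Name treatment burden and symptom burden separately so that the rule is unambiguous.
3. Reconcile the baseline text in 13.1 with the schedule in 13.2 on stress and mood, and add symptom burden to the schedule. Apply ANCOVA to these three if they are collected at enrolment.
4. State that the contact 2 (week -1) reading is not used as a baseline, because it follows randomisation.

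The cost is a sentence or two of text and a clerical correction to the schedule. No new data are needed, and the change can be made at any stage of recruitment, provided it is fixed before outcomes are compared by arm. Adding a withdrawal scale at enrolment is not part of this fix: it would be a new data item, and it would be missing for anyone already randomised.

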4.0 Number of Participants

4.1 Total number of participants to be accrued. Up to 82 adult participants will be enrolled in the clinical trial by UW-CTRI staff from UW Carbon Cancer Center clinic referrals over 12-30 months. We will continue enrolling within each clinic until we reach saturation in qualitative data analysis of patient interviews (maximum N=32) and until we reach our target enrollment for the CET (N=50).

4.2 Number of participants needed to complete the research procedures. We anticipate that we will engage 12% of participants in some form of evidence-based treatment, and that 50 will enroll in the proposed comparative effectiveness study while another 50 will opt for the Wisconsin Tobacco Quit Line. As such, we anticipate that we will need to reach out to approximately 833 patients who meet criteria to be included on the quarterly CRDS reports that will guide proactive outreach letters and calls. We anticipate that the remaining 733 participants will either opt-out of smoking treatment outreach, will not be reached by the outreach team, will decline tobacco treatment, will elect to pursue treatment via their primary care provider or other means (e.g., over-the-counter) rather than to use formal treatment, or will not complete the treatment enrollment process for other reasons.

Among the 50 participants who enroll in the CET, we will use an intent-to-treat approach to data analyses so that all randomized participants will be included in key analyses of feasibility, acceptability, and abstinence rates, even if lost to follow-up. In primary analyses of abstinence outcomes, missing cases will be treated as still smoking. This will be supplemented by sensitivity analyses under varying assumptions regarding censored data (i.e., that 5%, 10%, or 20% of missing data are abstinent).

For the qualitative interviews, even 2-5 interviews could inform and enhance study methods. We anticipate that we could reach thematic saturation in qualitative data coding with fewer than 32 interviews, and have set 32 as an upper limit for recruitment.

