The only biospecimens to be collected in the study will be collected directly from CET participants at the follow-up visit 6 months after a participant's target quit date, if the participant reported no use of tobacco products at the 26-week post-quit-date follow-up call. These participants reporting abstinence from tobacco will be asked to provide a breath sample for CO testing and a single urine sample for cotinine testing at either the UW-CTRI Madison office or at their oncology clinic (if willing to schedule this so it coincides with a clinic visit). Breath samples cannot be stored and urine samples will be tested immediately after collection and then discarded the same day. If patients are unable to travel to Madison for biochemical verification of abstinence, they will be given the option of providing a saliva sample in the mail using a kit supplied by the research team. These kits would be retained only until testing by a lab is complete and would then be destroyed.

3. Drugs.

The medications to be used in this study include transdermal nicotine patches and varenicline. Both medications are approved by the FDA for use as smoking cessation aids. No other medications or devices will be used in the research.

13.4 Data Collection.

• List of data elements.

The following data elements will be extracted from EHR data via CRDS reports. These data elements are needed to enable preparation of initial study recruitment mailings that will let patients know they have been identified for the study and that they can opt out of recruitment calls and letters.

- MRN
- Name
- Phone numbers (with preferred number flagged)
- Address
- City
- State
- ZIP code
- Communication preferences (MyChart, mail, phone)
- Tobacco use status (must be smoking currently)

PROTOCOL TITLE: Comparative Effectiveness Trial of Tobacco Cessation Treatments among Cancer Patients who Smoke

- Preferred language (must be English or missing)
 - Use of smokeless tobacco
 - Use of e-cigarettes
 - Date of birth (must be at least 18 years old)
 - Sex
 - Gender
 - Race
 - Ethnicity
 - Insurance type
 - Assigned primary care provider
 - Oncologist
 - Clinic department (where seen in the past year to achieve eligibility)
 - Cancer diagnosis (diagnosis in past 3 years that conferred eligibility)

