17.0 Provisions to Protect the Privacy Interests of Participants

17.1 Steps to protect participants' privacy interests. If any of the following apply, check the box for convenience:

- Procedures will be performed in a private area where others cannot see the procedures being performed or overhear the conversation between subjects and researchers.
- All members of the study team are up to date on their institutional HIPAA training.
- The study is not collecting information that could pose legal or reputational risks to participants.

Almost all study activities (apart from biochemical verification visits) will occur by phone. To protect participant privacy, study coordinators will encourage participants to move to private spaces during recruitment and study calls, and will offer to reschedule calls if participants are unable to do so.

Biochemical verification tests will happen in private spaces, as well (CO tests will be conducted in private rooms and urine samples will be self-collected by participants in private restrooms, without staff observation).

17.2 Sensitive information.

The only sensitive information to be collected in the study is self-reported use of cannabis. This information is needed to assess concurrent use of cannabis that may influence smoking cessation success and to interpret carbon monoxide and cotinine tests that

PROTOCOL TITLE: Comparative Effectiveness Trial of Tobacco Cessation Treatments among Cancer Patients who Smoke

could be influenced by use of combustible cannabis (in the case of CO) and use of cannabis in tobacco leaf wrappers (in the case of CO and cotinine).

17.3 Steps to make the participants feel at ease.

Collection of sensitive information about subjects will be limited to the amount necessary to achieve the aims of the research and to interpret biochemically verified abstinence data correctly.

Participants will be informed that they have the right to decline to answer any question they prefer not to answer, without penalty or punishment, and that the study has a Certificate of Confidentiality.

17.4 Authorized access to UW Health records.

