No formal inferential interim analyses are planned for this pilot study, but safety data will be examined on an on-going basis to determine if individual participants are at risk or if any treatment element or condition is exerting an iatrogenic effect. If any meaningful evidence of this is detected the DSMC will be consulted along with the IRB to consider study discontinuation or changes. If any danger is deemed likely and significant the study will be immediately suspended.

20.6 Handling of Missing Data. The intent-to-treat principle will be applied to primary analyses. Patients who do not initiate smoking treatment via a UW-CTRI study coordinator will be assumed to not have initiated treatment. In analyses of abstinence, cases who do not report abstinence and provide biochemical evidence of abstinence will be coded as still smoking in primary analyses. This will be supplemented by sensitivity analyses to estimate treatment effects under different assumptions regarding missing data (e.g., if 10%, 20% or 30% of people without verified abstinence are abstinent).

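### Sections 4.2 and 20.6 give conflicting missing-data sensitivity analyses, and the 20.6 rule as worded, with one common share, cannot test missingness

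*Combined protocol and SAP*

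**What the plan says.** The primary analysis is stated consistently. Section 4.2: "In primary analyses of abstinence outcomes, missing cases will be treated as still smoking". Section 20.6 is slightly broader: "cases who do not report abstinence and provide biochemical evidence of abstinence will be coded as still smoking in primary analyses".

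The supplementary analyses are described three times:

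- Section 4.2 plans "sensitivity analyses under varying assumptions regarding censored data (i.e., that 5%, 10%, or 20% of missing data are abstinent". The list is introduced by *i.e.*, so it reads as the definition, and the base is missing cases.
- Section 20.6 considers what happens "if 10%, 20% or 30% of people without verified abstinence are abstinent". The list is introduced by *e.g.*, and the base is everyone whose abstinence was not verified.
- Section 20.2 states the purpose, to "examine robustness of results across different assumptions regarding missingness", and rules out multiple imputation.

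Section 13.3 (Biospecimens) says a sample is collected only "if the participant reported no use of tobacco products at the 26-week post-quit-date follow-up call". No section gives arm-specific shares, narrows the 20.6 base or reconciles it with 4.2.

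**The concern.** Two analysts could follow the plan faithfully and run different checks on the primary endpoint. The mismatch in percentages is minor, since 10% and 20% appear in both lists. The mismatch in base is not.

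Because samples are sought only from people who report abstinence, anyone who reports smoking at week 26 is unverified by design. Read literally, 20.6 would relabel some of these people as abstinent although their outcome was observed. With the same share in both arms, the number missing per arm then drops out of the calculation and the direction of effect is fixed in advance. A reader who saw the direction hold across 10%, 20% and 30% could take that as robustness to loss, when it follows from the arithmetic.

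Unequal loss is a realistic possibility. Enhanced care has seven calls running to week 12 and standard care has three ending at week 1 (section 11.1), and sections 3.3 and 20.1 expect better retention in enhanced care. That expectation concerns treatment, not week-26 follow-up, but coding missing as smoking would favour whichever arm is better followed. The effect estimate is meant to guide a full-scale trial (section 20.2).

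**Working it through.** The plan gives no numerical result for this analysis to reproduce and no expected week-26 loss by arm. Follow-up rates and counts below are therefore assumptions. From the plan: 25 participants per arm (4.3), odds ratio and number needed to treat as effect measures (20.4), and cited cancer-trial abstinence rates of 34.5% and 21.5% (2.5).

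**Formulas.** Let p be the proportion verified abstinent in an arm, m the proportion missing, f the common share, and E and S the enhanced and standard arms.

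- 20.6 read literally: p′ = p + f(1 − p). Hence RD′ = (1 − f)·RD, NNT′ = NNT/(1 − f) and OR′ = (odds_E + f)/(odds_S + f). Neither m appears, and OR′ stays on the same side of 1 as OR. The rescaling is exact for RD and NNT; for the OR it is a nonlinear shrinkage toward 1.
- Missing cases only (the 4.2 base): p′ = p + f·m. Hence RD′ = RD + f(m_E − m_S).

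**Cited rates, 34.5% vs 21.5%.** RD 0.130, OR 1.92. Under 20.6 at 10/20/30%: RD 0.117, 0.104, 0.091; OR 1.68, 1.53, 1.44. The RD multipliers are exactly 0.90, 0.80 and 0.70.

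**Does missingness enter?** Assume 9/25 vs 5/25 verified (RD 0.160). Under 20.6, RD is 0.144, 0.128, 0.112 whatever the missing counts. Under 4.2 at 5/10/20%:

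- missing 5 vs 5: 0.160 throughout
- missing 2 vs 12: 0.140, 0.120, 0.080
- missing 8 vs 2: 0.172, 0.184, 0.208

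**No true effect, unequal loss.** Assume true abstinence of 25% in both arms and missing at random, so p = 0.25 × follow-up rate. At 90% vs 70%, p is 0.225 vs 0.175 and OR = (0.225/0.775)/(0.175/0.825) = 1.37.

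| Follow-up, E vs S | Primary OR | 20.6 at 10/20/30% | Missing-only at 10/20/30% |
|---|---|---|---|
| 80% vs 80% | 1.00 | 1.00/1.00/1.00 | 1.00/1.00/1.00 |
| 90% vs 80% | 1.16 | 1.12/1.09/1.07 | 1.09/1.03/0.97 |
| 90% vs 70% | 1.37 | 1.25/1.19/1.15 | 1.19/1.06/0.95 |
| 70% vs 90% | 0.73 | 0.80/0.84/0.87 | 0.84/0.95/1.05 |

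The missing-only column uses the 20.6 shares so that only the base differs. The 4.2 rule itself, at 5/10/20%, gives 1.27/1.19/1.06 for 90% vs 70%. There RD′ = 0.05 − 0.20f, which is zero at f = 25%, just beyond the largest share in 4.2.

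Sensitivity to the assumed rate, at 90% vs 70% follow-up and true abstinence of 21.5%, 25%, 30% and 34.5%:

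- primary OR: 1.35, 1.37, 1.39, 1.41
- 20.6 at 30%: 1.13, 1.15, 1.18, 1.21
- missing-only at 30%: 0.91, 0.95, 1.00, 1.04

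**Worked counts.** Assume 25 per arm, 6 vs 5 verified, 2 vs 8 missing, and the rest reporting smoking (17 vs 12). The primary OR is (6/19)/(5/20) = 1.26.

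- 20.6 at 10/20/30%: 1.19, 1.15, 1.12. At 30% it relabels 0.3 × 17 = 5.1 and 0.3 × 12 = 3.6 known smokers as abstinent.
- Missing-only at 10/20/30%: 1.09, 0.96, 0.85. The direction changes at f = (6 − 5)/(8 − 2) = 17%.
- Shares of 0–50% set separately by arm: from (6/19)/(9/16) = 0.56 to (7/18)/(5/20) = 1.56.

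**Sampling error.** For 5.625 vs 4.375 expected quitters per 25 (the 90% vs 70% case), SE(log OR) = √(1/5.625 + 1/19.375 + 1/4.375 + 1/20.625) = 0.71, giving a 95% CI of about 0.34 to 5.5.

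**The case against.** The best reply is that 20.6 is loosely worded. It is headed as missing-data handling and calls its scenarios assumptions about missing data, so its base may be shorthand for missing or unsampled cases. It does not say the share must be the same in both arms, and *e.g.* makes its percentages illustrative. The rescaling result needs both the literal base and a common share. That stands as a condition. It does not remove the problem, because nothing in the text excludes reported smokers or sets shares by arm.

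Section 4.2 is also not a full test. With a common share and equal loss it leaves the risk difference unchanged, and in the follow-up scenarios above the direction changes only at 30%, a missing-only share that 4.2 does not reach. This is right, and it is why arm-specific shares and a wider range are needed.

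Nor is 20.6 always the less cautious rule. With 9 vs 5 verified and 4 vs 8 missing it gives 1.89/1.69/1.57, against 1.99/1.80/1.64 for missing-only at the same shares. In the unequal-loss null scenarios it does move the estimate toward 1.

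Section 16.5 describes those offered saliva kits by no smoking in the past 7 days, not by no tobacco use. On either wording, people who report smoking are not sampled.

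Finally, the primary estimate is untouched and sampling error exceeds the bias. Both points are correct and limit the severity. They do not justify a sensitivity analysis that cannot answer its stated question.

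**Conclusion.** The concern holds. Sections 4.2 and 20.6 conflict in shares and, more importantly, in base; this needs no assumption. On the literal reading of 20.6 with one common share, the analysis multiplies the risk difference by 0.90, 0.80 or 0.70, cannot change direction and ignores how many are missing in each arm, contrary to the purpose in 20.2.

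In practice, under the assumed 90% vs 70% follow-up and no true effect, the rules nearly agree at their lower shares and diverge at their largest (1.15 for 20.6, 1.06 for 4.2). In the assumed 6 vs 5 example they disagree on direction. These sizes depend on follow-up rates and counts that the plan does not give. The text should be corrected before analysis; the primary analysis does not need to change.

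**What to change.** State one rule and use it in both 4.2 and 20.6:

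- Keep missing = smoking as the primary analysis.
- In sensitivity analyses, impute only participants whose week-26 status is unknown: no report, or reported abstinence with no usable sample. Keep self-reported smokers as smokers.
- Let the assumed share differ by arm, for example 0–50% in each, and report the tipping point.
- Report by arm the number with no report and the number reporting abstinence without a sample.

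Two optional additions are deaths by arm and a separate misclassification check for samples that fail to confirm abstinence. These stay non-abstinent in the primary analysis, but section 17.2 notes that cannabis use can affect CO and cotinine results.

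The cost is a few lines in the two sections and one small table, with no extra data collection.
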